Patients will be recruited in several ways. First, patients will be recruited through the RPDR. We will include patients who have and have not agreed to participate in RODY (Research Options Direct to You). Two different recruitment methods will be used to recruit “RODY yes” and “RODY no” patients.

“RODY No” patients identified from the RPDR will be sent an opt-out letter from their cardiologist and an accompanying letter from the study team. These letters (attached) will describe the study procedures and ask patients to contact the study team within 2 weeks if they would not like to be contacted to hear more about the study. Patients will have the option to opt-out via email. To address security issues related to email communication, participants will be informed about security in the opt-out letter itself and the following text will be included, “Please note that emails sent to the study staff from your personal email address may not be secure and could result in the unauthorized use or disclosure of your information. If you want to email the study team despite these risks, Partners HealthCare will not be held responsible. If you do not want to email the study team, you may instead call [contact]”. For any emails sent by the study team, they will be encrypted unless patients verbally agree to receive unencrypted emails. Patients will receive the following information: “The Partners HealthCare standard is to send email securely. This requires you to initially set up and activate an account with a password. You can then use the password to access secure emails sent to you from Partners HealthCare. If you prefer, we can send you “unencrypted” email that is not secure and could result in the unauthorized use or disclosure of your information. If you want to receive communications by unencrypted email despite these risks, Partners HealthCare will not be held responsible. Your preference to receive unencrypted email will apply to research studies for emails sent to you from research staff in this study. If you wish to communicate with other research staff at Partners regarding additional studies, your preference will have to be documented with each research

group." Those who do not opt-out will be contacted via phone by the PI or a trained and CITI-certified research staff member. Patients will be read a brief phone script (attached) informing them of the purpose of the call and asking if they would like to hear more about the research study. Those who agree will be read an information sheet detailing the study procedures, risks and benefits, and confidentiality, and inviting them to participate in the study.

"RODY Yes" patients will receive one opt-out letter from the study team. This letter (attached) will describe the study procedures and ask patients to contact the study team within 2 weeks if they would not like to be contacted further about the study. Those who do not opt-out will be contacted via phone by the PI or a trained and CITI-certified research staff member. Patients will be read a brief phone screen (attached), which will inform them of the purpose of the call and ask if they would like to hear more about the research study, and which will mention that they are being contacted because they agreed to be approached about clinical research studies. Those who agree will be read an information sheet (attached) detailing the study procedures and inviting them to participate. "RODY Yes" and "RODY No" patients will be read the same information sheet, though the opt out letter and phone script will differ.

Only the Principal Investigator and trained research staff will identify and contact patients. Up to approximately 10 calls will be made to a given patient, leaving up to approximately 3 voicemails, before assuming the patient is not interested and no longer attempt to contact them.

Second, patients will be recruited through advertisements (e.g., flyers, brochures) placed throughout inpatient and/or outpatient hospital clinics, community mental health clinics, and social media platforms. The advertisements will ask patients to contact study staff if they are interested in learning more about the study, and the screening procedures will be the same as those described above for RPDR patients. Flyers will also be posted in public areas throughout the community (e.g., coffee shop). In situations where a briefer ad is more feasible (e.g. virtual postings on iPads and computer screens in clinic waiting rooms), a shortened version of the flyer, detailing the study's purpose and contact information, will be posted. The flyers are included in the IRB submission. Specific phone numbers on the flyers will be filled in based on the contact information for the current RA.

Lastly, patients will be recruited via direct referrals from their providers (e.g., cardiologists, psychiatrists). We will inform providers about the study (e.g., via short presentations at their team meetings) and provide them with advertisement materials to give to their patients. The patients may either contact study staff directly using the information their provider gave them, and/or the provider will contact the study team with the patient's information so that the study team may reach out to the patient. Providers will obtain verbal permission from the patient for the research team to contact them.

Provide details of remuneration, when applicable. Even when subjects may derive medical benefit from participation, it is often the case that extra hospital visits, meals at the hospital, parking fees or other inconveniences will result in additional out-of-pocket expenses related to study participation. Investigators may wish to consider providing reimbursement for such expenses when funding is available

Participants will receive a \$30 gift card for participation in the study at the end of the focus group. Participants will also receive a \$20 check to provide reimbursement for the cost of travel and parking at the hospital, based on their provided receipts.

For guidance, refer to the following Partners policies:

Recruitment of Research Subjects

https://partnershealthcare-public.sharepoint.com/ClinicalResearch/Recruitment_Of_Research_Subjects.pdf

Guidelines for Advertisements for Recruiting Subjects

<https://partnershealthcare-public.sharepoint.com/ClinicalResearch/Guidelines%20For%20Advertisements.1.11.pdf>

Remuneration for Research Subjects

<https://partnershealthcare-public.sharepoint.com/ClinicalResearch/Remuneration%20for%20Research%20Subjects.pdf>

CONSENT PROCEDURES

Explain in detail how, when, where, and by whom consent is obtained, and the timing of consent (i.e., how long subjects will be given to consider participation). For most studies involving more than minimal risk and all studies involving investigational drugs/devices, a licensed physician investigator must obtain informed consent. When subjects are to be enrolled from among the investigators' own patients, describe how the potential for coercion will be avoided.

After identifying potential participants from the RPDR, the study team will mail patients the opt-out letters (one from the cardiologist and one from the study team for "RODY no" patients; one from the study team for "RODY yes" patients). For those who do not opt-out within two weeks, the principal investigator or a trained research staff will contact patients to read the study information sheet over the phone. The researcher will first briefly introduce themselves and the purpose of the phone call and, for patients who are interested in hearing more, the RA will begin the phone screening procedures (see attached phone screen document). For patients who meet eligibility criteria and are willing to hear more about the study, the researcher will review the information sheet (see attached). The information sheet will include a description of all study procedures and information about potential risks and benefits of participation. It will state that participation is voluntary, that participants can refuse to answer questions that make them uncomfortable, that participants can discontinue participation at any time, and that not completing the study will not compromise their medical care. Participants will be given the opportunity to ask questions about their participation throughout the course of their participation in the study. After reviewing the information sheet, the researcher will ask if patients have any remaining questions and then ask if they are interested in participating in the study. The RA will offer to mail a paper copy of the information sheet to the participant if they would like one.

For patient referrals that come to the study staff from the patient's provider, we will contact the patients using the same RODY phone screening materials and state that we are calling based on a referral from their doctor. Patients who contact study staff in response to advertisement materials will complete similar phone screening procedures as RODY patients and patient referrals. Along with the screening questions asked on the RODY/patient referral phone screen, patients recruited via social media will answer additional questions assessing their cardiac history (e.g., date of cardiac event, hospitalization, cardiologist) in order to ensure that the data they provide is amenable with the data extracted from the medical records of Partner's patients (see external recruit phone screening document). Participants will be informed that they can choose not to answer these questions. If patients who do not answer these questions are found to be eligible, the PI will contact them to explain that the qualitative research will inquire about these topics and determine their comfort and suitability for participating in the focus group or individual interview. For those who are found to be eligible, the consenting procedures will be the same as described above.

NOTE: When subjects are unable to give consent due to age (minors) or impaired decision-making capacity, complete the forms for Research Involving Children as Subjects of Research

and/or Research Involving Individuals with Impaired Decision-making Capacity, available on the New Submissions page on the PHRC website:

<https://partnershealthcare.sharepoint.com/sites/phrmApply/aieipa/irb>

For guidance, refer to the following Partners policy:

Informed Consent of Research Subjects:

[https://partnershealthcare-public.sharepoint.com/ClinicalResearch/Informed Consent of Research Subjects.pdf](https://partnershealthcare-public.sharepoint.com/ClinicalResearch/Informed%20Consent%20of%20Research%20Subjects.pdf)

DATA AND SAFETY MONITORING

Describe the plan for monitoring the data to ensure the safety of subjects. The plan should include a brief description of (1) the safety and/or efficacy data that will be reviewed; (2) the planned frequency of review; and (3) who will be responsible for this review and for determining whether the research should be altered or stopped. Include a brief description of any stopping rules for the study, when appropriate. Depending upon the risk, size and complexity of the study, the investigator, an expert group, an independent Data and Safety Monitoring Board (DSMB) or others might be assigned primary responsibility for this monitoring activity.

NOTE: Regardless of data and safety monitoring plans by the sponsor or others, the principal investigator is ultimately responsible for protecting the rights, safety, and welfare of subjects under his/her care.

For this exploratory study, there will not be interim analyses of samples. However, if it appears that patients do not find the planned research procedures to be acceptable, these procedures will be modified to align with patients' expressed preferences.

Describe the plan to be followed by the Principal Investigator/study staff for review of adverse events experienced by subjects under his/her care, and when applicable, for review of sponsor safety reports and DSMB reports. Describe the plan for reporting adverse events to the sponsor and the Partners' IRB and, when applicable, for submitting sponsor safety reports and DSMB reports to the Partners' IRBs. When the investigator is also the sponsor of the IND/IDE, include the plan for reporting of adverse events to the FDA and, when applicable, to investigators at other sites.

NOTE: In addition to the adverse event reporting requirements of the sponsor, the principal investigator must follow the Partners Human Research Committee guidelines for Adverse Event Reporting

All PHRC guidelines will be followed with respect to reporting unanticipated problems, including adverse events. Specifically, when a serious or non serious adverse event occurs, the PI will review the event to determine if it was possibly or definitely related to participation in the research. For all unanticipated problems and adverse events deemed related or possibly related to the research, a member of the research team will complete and submit an Other Event report through Insight/eIRB as soon as possible and within 5 working days / 7 calendar days (as defined in the March 2014 Reporting Unanticipated Problems Including Adverse Events report). At Continuing Review, a summary of all unanticipated problems will be provided as per PHRC protocol. Finally, if there are unanticipated

problems, especially if serious or recurrent, the PI will amend the protocol if it is deemed necessary to protect the safety and welfare of the participants.

MONITORING AND QUALITY ASSURANCE

Describe the plan to be followed by the principal investigator/study staff to monitor and assure the validity and integrity of the data and adherence to the IRB-approved protocol. Specify who will be responsible for monitoring, and the planned frequency of monitoring. For example, specify who will review the accuracy and completeness of case report form entries, source documents, and informed consent.

NOTE: Regardless of monitoring plans by the sponsor or others, the principal investigator is ultimately responsible for ensuring that the study is conducted at his/her investigative site in accordance with the IRB-approved protocol, and applicable regulations and requirements of the IRB.

On a weekly basis, the research team will meet to review study progress. At that time, the principal investigator will review information sheet documents, study forms, and procedures completed that week. The study team will also discuss any procedural difficulties, recruitment issues, and adverse events at this meeting (and before if needed). Investigators will also review information sheet documents and address acute issues in real time throughout the week.

Several measures will be taken to ensure the integrity of data collection/entry/analysis and the fidelity of our intervention. Transcriptions of focus group interviews or individual interviews will be periodically reviewed by the PI and study staff to ensure their accuracy. Furthermore, all transcribed interviews will be coded independently by two individuals, and all disagreements will be adjudicated by the PI.

For guidance, refer to the following Partners policies:

Data and Safety Monitoring Plans and Quality Assurance

[https://partnershealthcare-](https://partnershealthcare-public.sharepoint.com/ClinicalResearch/DSMP_in_Human_Subjects_Research.pdf)

[public.sharepoint.com/ClinicalResearch/DSMP_in_Human_Subjects_Research.pdf](https://partnershealthcare-public.sharepoint.com/ClinicalResearch/DSMP_in_Human_Subjects_Research.pdf)

Reporting Unanticipated Problems (including Adverse Events)

[https://partnershealthcare-](https://partnershealthcare-public.sharepoint.com/ClinicalResearch/Reporting_Unanticipated_Problems_including_Adverse_Events.pdf)

[public.sharepoint.com/ClinicalResearch/Reporting_Unanticipated_Problems_including_Adverse_Events.pdf](https://partnershealthcare-public.sharepoint.com/ClinicalResearch/Reporting_Unanticipated_Problems_including_Adverse_Events.pdf)

PRIVACY AND CONFIDENTIALITY

Describe methods used to protect the privacy of subjects and maintain confidentiality of data collected. This typically includes such practices as substituting codes for names and/or medical record numbers; removing face sheets or other identifiers from completed surveys/questionnaires; proper disposal of printed computer data; limited access to study data; use of password-protected computer databases; training for research staff on the importance of confidentiality of data, and storing research records in a secure location.

NOTE: Additional measures, such as obtaining a Certificate of Confidentiality, should be considered and are strongly encouraged when the research involves the collection of sensitive data, such as sexual, criminal or illegal behaviors.

As noted, these risks will be minimized by using participant ID numbers rather than identifying personal data on study documents or audio recordings, and by using locked cabinets/offices and password-protected databases to store personal information. Only study staff (the PI, the research assistant entering data) will have any access to personally identifiable information about participants, and such access will be limited only to information necessary to complete study tasks. Furthermore, the audiotaped recordings of the focus groups or individual interviews will be identified only with a number (with this number linked to identifying information that is kept in a password-protected database), will be stored in a password-protected folder on Partners' secure network, and will be destroyed once the time period for keeping research-related data has passed.

SENDING SPECIMENS/DATA TO RESEARCH COLLABORATORS OUTSIDE PARTNERS

Specimens or data collected by Partners investigators will be sent to research collaborators outside Partners, indicate to whom specimens/data will be sent, what information will be sent, and whether the specimens/data will contain identifiers that could be used by the outside collaborators to link the specimens/data to individual subjects.

N/A

Specifically address whether specimens/data will be stored at collaborating sites outside Partners for future use not described in the protocol. Include whether subjects can withdraw their specimens/data, and how they would do so. When appropriate, submit documentation of IRB approval from the recipient institution.

N/A

RECEIVING SPECIMENS/DATA FROM RESEARCH COLLABORATORS OUTSIDE PARTNERS

When specimens or data collected by research collaborators outside Partners will be sent to Partners investigators, indicate from where the specimens/data will be obtained and whether the specimens/data will contain identifiers that could be used by Partners investigators to link the specimens/data to individual subjects. When appropriate, submit documentation of IRB approval and a copy of the IRB-approved consent form from the institution where the specimens/data were collected.

N/A

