Describe explicitly the methods for ensuring the safety of subjects. Provide objective criteria for removing a subject from the study, for example, objective criteria for worsening disease/lack of improvement and/or unacceptable adverse events. The inclusion of objective drop criteria is especially important in studies designed with placebo control groups.

This study is a one-time focus group or individual interview lasting approximately 60-90 minutes. The main psychosocial safety concern related to patients in this study is suicidal ideation, since many participants have elevated depression symptoms. Subject safety regarding suicidal ideation will be ensured in several ways.

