First, eligibility criteria require that patients do not have active suicidal ideation at the time of enrollment, and that they have not been hospitalized for a psychiatric reason in the past year. Thus, it is not likely that participants will report suicidal ideation during the focus group or an individual interview. During the eligibility screening procedures, participants will be administered the Patient Health Questionnaire-9 (PHQ-9) over the phone. If any patient during phone screening endorses suicidality (i.e., PHQ-9 item 9 score above 0; "Over the past two weeks, how often have you been bothered by thoughts that you were better off dead or of hurting yourself in some way"), the RA will follow our standardized, published specific safety assessment protocol that our team has developed and used in prior funded studies of ACS patients with elevated depression symptoms. The protocol involves further assessing safety risks through a series of structured questions, with specific instructions at each step based on the patients' response. It will begin by clarifying the response to PHQ-9 item 9 (i.e., determining passive versus active suicidality). If patients endorse active suicidality, the RA will further assess safety risks (e.g., plan, intent, past suicide attempts). The RA will notify the PI (a licensed clinical psychologist), and patient's treatment providers about any active suicidal ideation. The licensed psychologist will be immediately paged to conduct further assessment and intervention with patients found to be at imminent risk. The licensed psychologist will inform the patient's primary treatment providers of the patient's symptoms, and assist with the obtainment of further evaluation and care as needed (e.g., through referral to outpatient treatment or to the emergency department [ED]), depending on the urgency of the situation. We will contact providers for Partners' patients. For patients outside Partners we will obtain the patient's location and address as needed based on the PI's clinical judgment in order to assist with the obtainment of further evaluation of care (e.g. by encouraging patients to discuss with their provider or by contacting emergency services in the patient's area if needed). In previous work by this research team, it has been extremely rare for an ACS patient to report active suicidality that requires intervention.

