Similar procedures will be followed if participants report suicidality during the focus group or individual interview, or endorse this PHQ-9 item when completing the survey measures before the focus group or individual interview begins. Focus group participants will be approached individually after the focus group by the PI or research assistant and further assessed for risk using the same protocol described above. As above, if any participants are found to be at imminent risk, the licensed psychologist will be immediately paged to conduct further safety assessments and assist with the obtainment of further evaluation and care as needed, including facilitating a referral to the ED if needed. The same procedures will be followed whether the focus group or individual interview is conducted in person or virtually.

Given that many participants will have elevated depression symptoms as part of the eligibility criteria, participants will be provided with an outline of resources for mental health care and guidelines for how to access this care.

FORESEEABLE RISKS AND DISCOMFORTS

Provide a brief description of any foreseeable risks and discomforts to subjects. Include those related to drugs/devices/procedures being studied and/or administered/Performed solely for research purposes. In addition, include psychosocial risks, and risks related to privacy and confidentiality. When applicable, describe risks to a developing fetus or nursing infant.

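### For focus groups, the only stated time to clarify a PHQ-9 item 9 endorsement is after the session, even when it was recorded on the survey beforehand

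*Protocol*

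**What the plan says.** The relevant text is in the Protocol, Research Design and Methods, under the prompt on methods for ensuring the safety of subjects. It opens by stating the priority: "The main psychosocial safety concern related to patients in this study is suicidal ideation".

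Screening comes first. "During the eligibility screening procedures, participants will be administered the Patient Health Questionnaire-9 (PHQ-9) over the phone". A score above 0 on item 9 starts a structured safety assessment, described as published and used in the team's earlier studies. Its first step is stated: "It will begin by clarifying the response to PHQ-9 item 9 (i.e., determining passive versus active suicidality". Questions on plan, intent and past attempts follow if the ideation is active, and the licensed psychologist is paged at once for anyone found to be at imminent risk.

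The text then turns to the session and names two triggers in one sentence. The first: "Similar procedures will be followed if participants report suicidality during the focus group or individual interview". The second applies if they "endorse this PHQ-9 item when completing the survey measures before the focus group or individual interview begins". The next sentence gives the time for focus groups: "Focus group participants will be approached individually after the focus group by the PI or research assistant and further assessed for risk". That assessment uses the same protocol as phone screening, and the psychologist is again paged if imminent risk is found.

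The SAP lists the PHQ-9 among the survey measures and plans descriptive statistics. It does not deal with the handling of item 9.

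**The concern.** The two triggers differ in when the information becomes available. A disclosure made in front of peers arises mid-session, and a private approach once the group ends is a sensible way to respond. A survey answer is in hand before the group starts, and the protocol states no reason for holding it until the end.

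What is deferred is the first triage step, the one that separates passive from active ideation. The page to the psychologist depends on that assessment, so it is deferred too. The survey item is also the only scheduled check for a change since the phone screen. At stake is the prompt use of that answer on the risk the protocol itself ranks as its main psychosocial safety concern.

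**Working it through.** No formula in the plan needs reproducing. The check is to set the safety passages side by side and see whether any of them requires an earlier look at item 9.

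1. **Triggers and timing.** The session paragraph lists both triggers, then gives a single time for focus group participants, after the group. It makes no exception for the survey trigger.
2. **What the deferred assessment contains.** It is the phone-screening protocol, whose first step is the passive/active distinction. The statement that participants are further assessed therefore does not imply that this distinction was already made.
3. **Other places that might require an earlier check:**
   - The item on how risks are minimized (Research Design and Methods) and Foreseeable Risks and Discomforts make a psychologist or psychiatrist available during sessions, for discomfort or questions about the study. Neither says that anyone has read item 9 by then.
   - The phone-screening paragraph excludes active ideation, but as of enrollment: "eligibility criteria require that patients do not have active suicidal ideation at the time of enrollment". It cannot cover a later change.
   - Monitoring and Quality Assurance says investigators deal with acute issues as they arise. This is general and does not call for a survey check.
4. **Length of the wait.** Inputs: focus group length, about 60 to 90 minutes (Protocol, focus groups paragraph and safety text); the interval from survey completion to the start of the group, which is not given. Wait = interval + group length. With an interval of 0 or more, the wait is at least 60 to 90 minutes. No upper bound can be derived.
5. **Number of people affected.** This cannot be computed. The documents give neither an item 9 endorsement rate nor the time between phone screen and session.
6. **Workload of an earlier check.** From the planned design: 4 groups × 8 = 32 places for patients with elevated symptoms; 1 × 6 = 6 up to 2 × 8 = 16 places for those without. The total is 32 + 6 = 38 to 32 + 16 = 48 surveys, over 4 + 1 = 5 to 4 + 2 = 6 groups. This counts surveys to be read, not people at risk.

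**The case against.** The strongest reply concerns the reading. The sentence that introduces both triggers says similar procedures will be followed, and the procedures it points back to contain no delay. The after-group sentence could be meant only for disclosures made in the group, and it does not forbid an earlier approach. This stands as a possible reading. It does not remove the point, because the only time written down is after the group and staff have no other instruction in the documents.

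Second, the safety assessment protocol is not among the documents and may say when item 9 is to be read. That also stands, and it limits how firmly the point can be put.

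Third, the practical risk is low. Item 9 is asked at screening, any score above 0 is clarified then, and active ideation is an exclusion. Someone who endorses the item on the survey is therefore either a person already cleared or one whose state has changed since. During the wait the participant is in a session with a clinician available, and the team reports that "it has been extremely rare for an ACS patient to report active suicidality that requires intervention". All of this stands and sets the level of the point.

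Fourth, an earlier check has drawbacks: the start may slip, peers may notice someone being taken aside, and clinician availability is documented only during sessions, not in the minutes before them. These are costs of the fix, not reasons to leave the wording as it is.

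A reader might go further and infer that the protocol obliges staff to sit on a known warning, or that people with active ideation are likely to go unassessed through a group. The documents support neither: the text sets a default time without prohibiting earlier action, and the screening makes such a case unlikely. A reader might also extend the delay to individual interviews. The after-group sentence covers focus groups only, and no delay is set for interviews.

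**Conclusion.** The point holds as a cheap improvement to the wording of a safety rule. On its plain reading, the protocol lets the passive/active clarification of an answer already in hand wait at least one session, about 60 to 90 minutes. The remaining exposure is a participant whose state changed between the phone screen and the survey.

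The conclusion rests on two assumptions: that the after-group sentence applies to both triggers as written, and that the unseen safety assessment protocol does not set an earlier time. If either fails, the change only states what was already intended. Putting a figure on expected harm would need an endorsement rate that the documents do not give, so none is offered.

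**What to change.** Limit the after-group sentence to suicidality reported during the group itself, and add:

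> Staff will read PHQ-9 item 9 when each survey is completed and before the focus group starts. Any score above 0 will be clarified privately as passive or active by the PI or research assistant, using the protocol above, before the group begins. If active ideation is found, that protocol is followed at once and the PI decides whether the participant joins.

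A matching line for individual interviews would be an optional clarification only.

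**Cost.** A short text change, an IRB amendment, and one item read on about 38 to 48 surveys across the planned groups. No new measure or assessment tool is needed. The PI or licensed psychologist should be reachable shortly before each group, which the protocol does not now state. A short start delay and peers noticing are the real downsides. Staggered arrival, or a separate call for virtual groups, reduces both.
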